7.2 Rationale

Subjects in the METEOR study were included under controlled conditions (strict inclusion and exclusion criteria, guidelines for therapy management, monitoring of compliance). In the real-world setting, the same criteria will not apply and the utilisation pattern of cabozantinib is unknown. Prevalent practice patterns may call for implementation of new measures to optimise the use of cabozantinib in RCC.

Published data with VEGFR-targeted therapies reported that a number of subjects start the treatment with doses or regimens that are different from the standard dosing [8, 9]. The rate of subjects using cabozantinib with schedules or dosing different from the recommended regimen at initiation (60 mg/day) and the tolerability of cabozantinib in second versus third and later lines in the real-life setting are unknown.

For this prospective study, the primary endpoint is to describe the proportion of subjects with dose modifications due to AEs based on the investigator's decision (temporary interruption, dose reduction or discontinuation) when cabozantinib is used as a second line therapy or third and later line therapy.

PAGE 23 OF 58

8 RESEARCH QUESTION AND OBJECTIVES

8.1 Research Question

For this prospective study, the objective is to understand the utilisation of cabozantinib in subjects with advanced RCC following prior VEGF-targeted therapy in real-life settings in terms of dose modifications due to AEs when used as a second line therapy or third and later line therapy. Other patterns of use of cabozantinib will also be described as listed in the study objectives.

8.2 Objectives

8.2.1 Primary Objective:

• To describe the pattern of dose interruptions, reductions or discontinuations of cabozantinib due to AEs in clinical practice when used as a second or third and later line therapy.

8.2.2 Secondary Objectives:

- To describe the use of cabozantinib in subjects with advanced RCC treated in real-life clinical settings;
- To describe all treatment-emergent nonserious and serious AEs;
- To describe the effectiveness of cabozantinib in RCC in real-life in terms of PFS and best overall response;
- To describe the health care resource utilisation associated with the management of treatment-related AEs during the treatment period (hospitalisation, surgical procedures, emergency room visits, intensive care unit stays, concomitant medications, physician visits and homecare visits by nurse, unplanned laboratory tests).

PAGE 24 OF 58

9 RESEARCH METHODS

9.1 Study Design

This is a prospective, international, multicentre, noninterventional study.

9.2 Setting

The study will include subjects diagnosed with advanced RCC, having received at least one prior VEGF-targeted therapy, who are starting treatment with cabozantinib tablets at the discretion of the treating physician in the clinical setting (not as part of an interventional clinical study).

A total of 680 subjects are to be included in the study in countries where cabozantinib is marketed at the time of the study. It is planned to include equal numbers of subjects receiving second line therapy and third and later line therapy.

The study will follow the real-life management of patients in clinical practice. Visits will take place according to the study site's clinical practice. Cabozantinib is to be administered as directed by the investigator according to the study site's usual clinical practice and the Cabometyx™ Summary of Product Characteristics (SmPC). Only available evaluations as decided by the investigator based on local clinical practice will be collected. The investigator will report data for study endpoint assessments during the study data reporting periods (see Table 1 for a summary of the schedule of assessments to be reported).

9.2.1 Inclusion Criteria

To be included in the study, the subject should fulfil all the following inclusion criteria:

- (1) Age \geq 18 years old;
- (2) Has a diagnosis of advanced RCC;
- (3) Has received at least one prior VEGF-targeted therapy;
- (4) For whom the treating physician has decided to start treatment with cabozantinib tablets prior to inclusion;
- (5) No previous exposure to cabozantinib prior to inclusion;
- (6) Not concurrently involved in an interventional study;
- (7) Consents to participate in this noninterventional study.

9.2.2 Exclusion Criteria

There are no exclusion criteria for this study.

9.2.3 Study Population

The study population will consist of subjects diagnosed with advanced RCC, having received at least one prior VEGF-targeted therapy, who are starting cabozantinib tablets at the discretion of the treating physician and who consent to participate in the study.

In order to avoid bias related to physician-led subject selection, participating physicians will be asked to include all successive eligible subjects except those who refuse the collection of and/or access to their data until 340 subjects have been included in each subgroup (second and third and later line therapy).

9.2.4 Study Duration

In the METEOR study, the median duration of exposure in subjects receiving cabozantinib was 8.3 months (Inter-Quartile Range 4.2 to 14.6).

PAGE 25 OF 58

Subjects will be followed up to 30 days after discontinuation of cabozantinib with a maximum follow-up per subject of 12 months from treatment initiation, even if the subject continues to receive cabozantinib.

The end of the study will be the date of the last study visit for the last subject in the study.

9.2.5 Study Place

Subjects will be recruited in countries where cabozantinib is marketed at the time of the study. It is anticipated that there will be approximately 100 study centres in 10 to 15 European countries. The number of sites in each country will be decided according to the size of the country.

Study centres will be proposed by the sponsor's local medical teams. Successive proposed sites that meet the feasibility criteria will be selected.

9.2.6 Study Schedule

The schedule of assessments to be reported is presented in Table 1.

In this noninterventional study, cabozantinib is to be administered as directed by the investigator according to the study site's usual clinical practice. The physician should refer to the Cabometyx TM SmPC for any information on the treatment prescribed.

Only available evaluations as decided by the investigator based on local clinical practice will be collected in the study. The most recent assessments available before each visit (including the inclusion visit if applicable) will be reported for 12-lead electrocardiograms (ECGs) and radiographic tumour assessments.

PAGE 26 OF 58

 Table 1
 Schedule of Assessments to be Reported

	Inclusion visit/ Treatment initiation Visit 1a	Visit 2 ^a	Visit 3 ^a	Visit 4 ^a	Visit 5 ^a	Visit 6ª	Visit 7ª	Visit 8ª	End of study visit Visit 9 ^a
Data reporting period (1 month=30 days)	D1	From D2 up to D30	Any time point from D31 up to D60	Any time point from D61 up to D90 (Month 3)	Any time point during Month 4 or Month 5	Any time point during Month 6 or Month 7	Any time point during Month 8 or Month 9	Any time point during Month 10 or Month 11	Any time point after Month 11 ^b
Assessments									
Signed informed consent	X								
Eligibility criteria	X								
Demographics, tobacco, occupational status, sick leave status	x								
Medical history, RCC cancer history and previous anticancer therapy	Х								
Planned frequency of radiological assessments	X								
ECOG performance status, height ^c , weight, vital signs	X	X	X	X	X	X	X	Х	X
12-lead ECG ^d	As available ^e	ECG performed according to local standards of care as clinically indicated ^f							
Clinical laboratory tests by local laboratory ^d		Clinical laboratory test to assess safety performed according to local standards of care as clinically indicated ^f							
Radiographic tumour assessment	As available ^e	Radiographic assessment performed according to local standards of care as clinically indicated ^f							
Concomitant medication	X	X	X	X	X	X	X	X	X
Radiotherapy/surgery	X ^g	X	X	X	X	X	X	X	X
Adverse events	X	X	X	X	X	X	X	X	X
Dose and schedule of cabozantinib prescribed	X	Х	x	X	X	Х	X	х	x^{h}
Cabozantinib dose modifications		X	X	X	X	X	X	X	$\mathbf{x}^{\mathbf{h}}$
Health care resource utilisation	X	X	X	X	X	X	X	X	x

PASS PROTOCOL: FINAL V 3.0: 21 JULY 2017 PAGE 27 OF 58

	Inclusion visit/ Treatment initiation Visit 1a	Visit 2ª	Visit 3ª	Visit 4ª	Visit 5ª	Visit 6ª	Visit 7ª	Visit 8ª	End of study visit Visit 9 ^a
Data reporting period (1 month=30 days)	D1	From D2 up to D30	Any time point from D31 up to D60	Any time point from D61 up to D90 (Month 3)	Any time point during Month 4 or Month 5	Any time point during Month 6 or Month 7	Any time point during Month 8 or Month 9	Any time point during Month 10 or Month 11	Any time point after Month 11 ^b
Assessments									
Study discontinuation or completion form		In case of	In case of permanent treatment discontinuation (approximately 30 days after the last dose of cabozantinib) i					cabozantinib) i	х

Abbreviations: AE=adverse event, D=day, ECG=electrocardiogram, ECOG=Eastern Cooperative Oncology Group, eCRF=electronic case report form, RCC=renal cell carcinoma, SAE=serious adverse event

- a. Visits will take place according to the study site's clinical practice. The investigator will report data for study endpoint assessments during each data reporting period. Only available evaluations as decided by the investigator based on local clinical practice will be collected. Where there are no data to report, this should be indicated in the applicable section(s) of the eCRF. In the case of more than one visit occurring during the data reporting period, the visit closest to the end of the period should be used for reporting purposes.
- b. The closest visit to Month 12 should be recorded as End of study Visit
- c. Height will be recorded at Visit 1 only.
- d. Any clinically significant abnormal value observed for laboratory tests and ECGs will be collected and reported as AEs or SAEs
- e. The most recent evaluations performed before initiation of treatment.
- f. The most recent assessment available before each visit.
- g. Only concomitant radiotherapy will be collected (i.e., prior radiotherapy will not be collected).
- h. If applicable
- i. In case of permanent treatment discontinuation between Visit 2 and Visit 8, the next visit should be completed along with the Study discontinuation form, approximately 30 days after the last dose of cabozantinib.

PAGE 28 OF 58

9.2.7 Study Visits

Visits will take place according to the study site's clinical practice.

The investigator will report data for study endpoint assessments during each data reporting period (see Table 1 and Section 9.3). In the case of more than one visit occurring during the data reporting period, the visit closest to the end of the period should be used for reporting purposes.

The data reporting periods are:

- Visit 1 (inclusion visit/treatment initiation) on Day 1;
- Visit 2: any time point from Day 2 up to Day 30;
- Visit 3: any time point from Day 31 up to Day 60;
- Visit 4: any time point after Day 61 up to Day 90 (Month 3);
- Visit 5: any time point during Month 4 or Month 5;
- Visit 6: any time point during Month 6 or Month 7;
- Visit 7: any time point during Month 8 or Month 9;
- Visit 8: any time point during Month 10 or Month 11;
- Visit 9 (End of study visit): any time point after Month 11 (ie, the closest visit to Month 12).

9.2.8 Study Discontinuation/Withdrawal

If the subject permanently discontinues cabozantinib before Month 12, he/she will be withdrawn from the study.

The investigator may withdraw the subject from the study at any time for safety reasons or at his/her discretion. A subject may withdraw consent to participate in the study at any time.

In case of permanent treatment discontinuation between Visit 2 and Visit 8, the next visit should be completed along with the Study discontinuation form, approximately 30 days after the last dose of cabozantinib (see Table 1 and Section 9.2.7).

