A planned interim analysis of OS conducted at the time of the PFS analysis [5] demonstrated a trend for longer OS for subjects in the cabozantinib arm compared with the everolimus arm: the HR for death was 0.67 (unadjusted 95% CI: 0.51, 0.89; p=0.005). The p-value of \leq 0.0019 required to achieve statistical significance at the time of the interim analysis was not reached. In a subsequent unplanned interim analysis of OS [6], a statistically significant difference in duration of OS for subjects in the cabozantinib arm compared with the everolimus arm was demonstrated (critical p-value from the alpha spending function of \leq 0.0163): the HR was 0.66 (95% CI: 0.53, 0.83; stratified logrank p=0.00026). Kaplan-Meier estimates of median duration of OS were 21.4 months in the cabozantinib arm and 16.5 months in the everolimus arm, an estimated 4.9 month difference in the medians.

In the METEOR study, cabozantinib was initiated at 60 mg/day. If a subject experienced an unacceptable study treatment-related adverse event (AE), study treatment interruption or a dose reduction was allowed at the investigator's discretion. Following a treatment interruption, the subject could have resumed treatment if the AE resolved to \leq grade 1 or to

PAGE 22 OF 58

baseline values within 6 weeks. The study treatment could have been restarted at a reduced dose to avoid worsening AEs, if the AE was related to treatment or dose reduction was otherwise deemed clinically necessary.

Treatment with cabozantinib was associated with a significant rate of treatment-emergent AEs (TEAEs) in the METEOR study: 100% of subjects presented with at least one TEAE. The most common grade 3 or 4 TEAEs with cabozantinib were hypertension (15%), diarrhoea (11%) and fatigue (9%) and with everolimus were anaemia (16%), fatigue (7%) and hyperglycaemia (5%). The most common TEAEs (any grade) leading to dose reductions with cabozantinib were diarrhoea (16%), the palmar-plantar erythrodysesthesia syndrome (11%) and fatigue (10%) and the most common with everolimus were pneumonitis (4%), fatigue (3%) and stomatitis (3%) (data cut-off 21 May 2015).

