9.7.2.5.2 Secondary Endpoints and Evaluations

The secondary endpoints include the following:

- Description of the pattern of use of cabozantinib in real-life clinical settings:
 - starting dose and schedule
 - duration of cabozantinib treatment
 - treatment line
 - dose reductions and reasons
 - treatment interruption and reasons
 - treatment discontinuation and reasons
 - changes in the dose and schedule and reasons
 - concomitant radiotherapies
 - planned systemic therapy following cabozantinib discontinuation
 - median time to first dose modification due to AEs based on the investigator's decision (reduction, temporary interruption or discontinuation) together and for each component separately
 - mean and median daily dose of cabozantinib received, and dose intensity (average daily dose compared to starting dose)
 - mean and median numbers of any dose modification (reduction, temporary interruption, increase or discontinuation)
 - median time to any first dose modification (reduction, temporary interruption, increase or discontinuation) together and for each component separately
 - median time to end of treatment;
- Effectiveness assessment:
 - overall best response per investigator assessment
 - clinical and radiographic (assessed by the investigator based on RECIST 1.1 [10]) median PFS time defined as the time between the start date of cabozantinib and the date of progression or death
 - OS rate at the end of the study;
- Description of health care resource utilisation associated with the management of treatment-related AEs (as assessed by the investigator as certain, probable, possible or unlikely) during the treatment period:
 - number and duration of hospitalisations
 - number of surgical procedures
 - number of emergency room visits and intensive care unit stays
 - number of physician visits
 - number of homecare visits by nurse
 - concomitant medication (initiation or change to manage AEs)

PAGE 35 OF 58

• number of unplanned laboratory tests.

The secondary endpoints will be provided in listing format using the FAS and summarised descriptively using the FAS or the Safety populations, as appropriate, by line of treatment and in total.

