In addition, the Kaplan-Meier method will be used to obtain the estimates of median PFS time, OS rate, median time to end of treatment, median time to first dose modification due to AEs based on the investigator's decision (temporary interruption, reduction or discontinuation) together and for each component separately and median time to any first dose modification (temporary interruption, reduction, increase or discontinuation) together and for each component separately and their associated 2-sided 95% CIs.

Concomitant medication will be coded using the World Health Organization Drug Dictionary (WHODRUG) and will be summarised with the number and percentage of subjects receiving concomitant medication by drug class and preferred drug name.

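### Follow-up stops about 30 days after the last cabozantinib dose, so the planned Kaplan-Meier OS rate does not estimate overall survival

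*Protocol*

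**What the plan says.** Section 9.2.8 of the protocol is explicit: "If the subject permanently discontinues cabozantinib before Month 12, he/she will be withdrawn from the study". The last data point after stopping is a single visit: "the next visit should be completed along with the Study discontinuation form, approximately 30 days after the last dose of cabozantinib". Section 9.2.4 sets the same window: "Subjects will be followed up to 30 days after discontinuation of cabozantinib with a maximum follow-up per subject of 12 months from treatment initiation". Footnote i of Table 1 agrees.

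Section 9.3.4 collects dates of progression and death, but only while the subject is in the study. Section 11 ends adverse event collection with the study, and the rapid-reporting rule in 11.1.4 concerns deaths during use of the product. No section asks for vital status after the post-treatment visit.

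Section 9.7.2.5.2 lists, under effectiveness, "OS rate at the end of the study" and "median PFS time defined as the time between the start date of cabozantinib and the date of progression or death". For both, "the Kaplan-Meier method will be used to obtain the estimates of median PFS time, OS rate, median time to end of treatment".

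The limitations in section 9.9 cover variation between sites and investigator assessment of response. They do not mention that length of follow-up depends on staying on treatment.

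**The concern.** Kaplan-Meier assumes that a subject censored at a given time has the same future risk as those still under observation. Here the main cause of censoring before Month 12 is that the subject stopped an anticancer drug about a month earlier. In advanced renal cell carcinoma, stopping commonly goes with progression, deterioration or intolerance, so equal future risk is doubtful. The curve would then describe mortality on the drug and shortly afterwards, carried forward to people who have left it, under the name of OS.

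This is a fault of data collection rather than of analysis detail. Deaths later than about 30 days after the last dose are not recorded, so no statistical analysis plan can recover them. A figure labelled OS in a post-authorisation study report may be quoted as real-world survival.

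**Working it through.** **The plan's own figures.** The protocol gives no expected value for OS. Its sample size rests on the primary proportion and reproduces: 1.96² × 0.75 × 0.25 / 0.05² = 288.1, so 289 per line; 289 / 0.85 = 340. OS plays no part in it.

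**Inputs from the protocol** (all from the pivotal METEOR study)
- Exposure: median 8.3 months, interquartile range 4.2 to 14.6 (section 9.2.4)
- Median OS 21.4 months and median PFS 7.4 months (section 7.1)
- Discontinuation for adverse events not related to the cancer: 9.7% (section 7.1)

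**Step 1. How many stop early.** Fit a Weibull distribution to the exposure quartiles:
- shape k = ln[ln 4 / ln(4/3)] / ln(14.6/4.2) = 1.262
- scale λ = 14.6 / (ln 4)^(1/k) = 11.27 months
- implied median λ(ln 2)^(1/k) = 8.4 months, against 8.3 stated
- P(stop within 11 months) = 1 − exp[−(11/11.27)^1.262] = 62%
- P(stop within 12 months) = 1 − exp[−(12/11.27)^1.262] = 66%

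Eleven months matters because 30 days later the 12-month cap applies anyway. Exposure ends for any reason, so a few of these subjects stop because they die.

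**Step 2. Effect on 12-month OS.** The link between stopping and death is not in the documents, so it is assumed and varied. In 400,000 simulated subjects, time to stopping follows the Weibull above. The death hazard is h on treatment and R × h after stopping, with h solved so that median OS is 21.4 months. Follow-up ends at the earlier of stopping plus 30 days and Month 12.

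| R | h per month | True 12-month OS | Kaplan-Meier | Overstatement (points) | Deaths by Month 12 missed |
|---|---|---|---|---|---|
| 1 | 0.0323 | 67.8% | 67.8% | 0 | 27% |
| 2 | 0.0212 | 71.1% | 75.9% | 4.8 | 40% |
| 3 | 0.0160 | 72.8% | 80.1% | 7.3 | 48% |
| 5 | 0.0108 | 74.4% | 84.4% | 10.0 | 57% |
| 8 | 0.0073 | 75.6% | 87.3% | 11.8 | 64% |

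The true value changes with R because each row is tied to the same median OS. A hand check shows the mechanism. At R = 2, on-treatment hazard alone gives exp(−12 × 0.0212) = 77.5%. The 30-day windows after stopping bring in a little of the higher hazard and lower this to 75.9%, still well above 71.1%.

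A second model links stopping and death by a Gaussian copula, with exponential survival of median 21.4 months. Correlations of 0.3, 0.5 and 0.7 give overstatements of about 4.4, 7.5 and 11.5 points. Zero correlation gives essentially none. A correlation of −0.3 gives an understatement of 4.6 points. Across both models, about 48% to 57% of subjects are censored for OS before Month 12.

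In both models death can also end treatment, so simulated exposure is somewhat shorter than the stated figures. The results show the order of magnitude only.

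**Step 3. Effect on PFS.** A progression that leads to stopping is recorded as an event, so only those who stop before progression are censored early. Suppose 9.7% stop first and then have 1 to 3 times the hazard of progression or death. The Kaplan-Meier median moves from 7.4 to at most 7.6 months, and 12-month PFS rises by 0 to 1.6 points. With 20% stopping first (an assumption), the median reaches at most 7.9 months and 12-month PFS rises by up to 3.4 points.

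**The case against.** The best defence is that OS is marginal here. Section 8.2.2 names only PFS and best overall response as effectiveness measures. OS is one line among the secondary endpoints, all analyses are descriptive, and the interim analysis changes nothing in the conduct of the study. The primary endpoint is dose modification due to adverse events, with discontinuation as a component, so ending follow-up afterwards takes nothing from it. All of this stands and limits the severity. It does not make the label correct.

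A second defence is that the bias rests on an assumed dependence. That also stands: the direction is expected but not documented, and the size can only be a range.

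Some stronger readings are tempting but unsupported:
- **An overstatement as large as 15 points.** This needs exponential exposure and only 5% of discontinuations being on-treatment deaths, which implies a death hazard after stopping about 16.6 times that on treatment. Exponential exposure with median 8.3 months also has quartiles of 8.3 × ln(4/3)/ln 2 = 3.4 and 8.3 × 2 = 16.6 months, against the stated 4.2 and 14.6.
- **Almost all deaths after progression are lost.** Deaths on drug or within 30 days are captured, and the protocol does not say that treatment ends at progression. The models miss a substantial share of deaths by Month 12, not nearly all.
- **Results would look better than METEOR.** The protocol gives no 12-month OS for METEOR and plans no comparison. This cohort has no exclusion criteria, is half third or later line, and need not have clear-cell histology, so its true survival may be lower.
- **The OS time point cannot be read.** Section 9.2.4 defines study end as a calendar date, but Table 1 and section 9.2.7 call each subject's visit nearest Month 12 the end of study visit. A Month 12 reading is natural; it only needs to be named.

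**Conclusion.** The point holds for OS. Treatment-dependent follow-up means that the planned Kaplan-Meier figure estimates overall survival only if stopping cabozantinib carries no information about later death. Under the assumption that the death hazard is 2 to 8 times higher after stopping, 12-month OS is overstated by about 5 to 12 points; the copula model gives about 4 to 12. The bias is zero if stopping and death are unrelated, and it reverses only if early stopping goes with longer survival, which is implausible here. Even without bias, about 27% of deaths by Month 12 would go unobserved. These sizes rest on METEOR exposure and survival carrying over to this cohort.

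PFS is only slightly affected and needs no extra analysis on this account. The endpoint should be fixed, but the primary objective is not at risk.

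**What to change.** Either of two changes is enough.

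1. **Collect the missing data.** Amend section 9.2.8 so that permanent discontinuation ends treatment but not data collection. Record vital status and date of death once from the medical record at Month 12 for every consenting subject. Replace the OS endpoint by the OS rate at Month 12. In the models above, Kaplan-Meier then returns the true value. The cost is one chart look-up per subject and a short amendment, within the existing 12-month window. It is best done before recruitment, since data on withdrawn subjects may be hard to recover later.

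2. **Rename what is collected.** With no new data, replace the OS rate by the cumulative incidence of death on treatment or within 30 days of the last dose, treating exit alive after that window as a competing event. Do not call it OS. Add treatment-dependent follow-up to the limitations in section 9.9. The cost is wording only; the downside is that the study then has no overall survival estimate.
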